10.2 Safety Monitoring and Mitigation Plan

Elevation of liver enzymes has been observed in other trials using AAV2/6. Therefore, liver tests (AST, ALT, bilirubin, alkaline phosphatase, and GGT) will be monitored closely throughout the study.

These will be performed twice weekly during the first 20 weeks after ST-920 infusion, weekly for four weeks (Weeks 21-24), and then monthly thereafter to coincide with study visits (Weeks 28-52) in all subjects, and may be conducted remotely.

If there is a need to initiate corticosteroid treatment as a result of elevated liver enzymes, liver enzymes will continue to be assessed at least twice a week until normalization and then per protocol thereafter analyzed locally or centrally.

10.3 Safety Monitoring Committee

An SMC with appropriate medical and scientific expertise was appointed to provide safety oversight for the study. The SMC is comprised of external subject matter experts, the study Medical Monitor, Sponsor's Drug Safety Lead, study Biostatistician, and Site Investigators as appropriate. The SMC will periodically meet during the study and provide recommendations to the Sponsor concerning dosing. The SMC will also convene at any time if an emergent safety issue emerges during the study or one of the stopping rules are met. These include:

- Any one Grade 3 or higher AE with at least a reasonable possibility of a causal relationship to the investigational product,
- Any SAE with at least a reasonable possibility of a causal relationship to the investigational product
- Death of a subject
- Development of a malignancy, with the exception of non-melanoma skin cancers and localized prostate cancer treated with curative intent

The study may also be stopped for any of the following reasons:

- Sponsor, in consultation with the SMC or Regulatory Agency, decides for any reason that subject safety may be compromised by continuing the study.
- Sponsor decides to discontinue the development of the investigational product, ST-920.

All data will be evaluated to determine whether changes should be made to the study or if accrual should be continued or halted. If stopping criteria are met, no further dosing of subjects will be performed at that dose level or higher until a substantial amendment is submitted to regulatory authorities for review, and the amendment has been approved by the site Institutional Review Board (IRB)/Independent Ethics Committee (IEC) or equivalent.

Relevant data from other trials sponsored by Sangamo may be shared with the SMC to expand the clinical experience, particularly as it relates to safety and dose, and such data can be used by the SMC to inform its recommendations for the present study.

The SMC may also recommend changes to the dose and enrollment of cohorts based on cumulative safety data from this and other Sangamo sponsored clinical trials that use *in vivo* AAV2/6-based therapy.

After the SMC meetings, the study sites will be informed of any decisions made in regards to the study and of any relevant safety data that might be helpful for subject treatment, follow-up and safety.

When no further enrolling or dosing decisions are required of the SMC, the SMC will no longer meet on a regular basis. The Sponsor will continue to review the subject safety data on an ongoing basis.

11 STATISTICAL ANALYSES

11.1 Determination of Sample Size

This study will enroll up to 48 subjects (2 subjects in each of Cohorts 1, 2, 3, and 4 with potential enrollment of 4 additional subjects in Cohorts 1, 2a, 2b, 3a, 3b, 4a, and 4b, plus up to 6 subjects in each of the anti α -Gal A Ab positive, anti α -Gal A Ab negative, female, renal, and cardiac cohorts). The sample size for this study was not based on statistical considerations but is considered sufficient to provide a preliminary assessment of the safety and tolerability of ST-920 in subjects with Fabry disease.

Subjects who prematurely discontinue the study prior to the 52 weeks of study follow-up (i.e., subjects who were enrolled but not dosed, were lost to follow-up, or discontinued prematurely for another reason) may be replaced at the discretion of the Sponsor.

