3 STUDY DESIGN

3.1 Overview and Rationale

This is a Phase I/II, multicenter, open-label, single-dose, dose-ranging study with a dose escalation phase potentially enrolling 4 cohorts representing 4 dose levels. Up to 48 subjects who are ≥ 18 years of age and who satisfy all inclusion/exclusion criteria are eligible to be enrolled in the overall study. Initially, recruitment will be limited to male subjects meeting criteria for inclusion during dose escalation. Once a safe and tolerable dose is selected, recruitment will be extended via dose expansion to a broader patient population. Once dose expansion is initiated, subjects will undergo assessments which will determine the most appropriate expansion cohort for their enrollment.

During dose escalation, treatment of the first 2 subjects will be staggered so that the subsequent subject cannot be infused until the preceding subject has been observed for at least 2 weeks. After any 2 subjects in a cohort have been dosed, safety data from these 2 subjects will be reviewed by the Safety Monitoring Committee (SMC). Dose escalation to the next dose cohort and dose expansion cannot occur until at least 4 weeks of safety data are available after the second subject in the preceding cohort has been dosed, and data from this cohort has been reviewed by the SMC. The SMC will recommend whether it is safe to escalate the dose or to add subjects to the dose cohort at the same dose level. Once a cohort's data has been reviewed and dose escalation has been endorsed, additional subjects may be infused at any time in the same cohort, as per protocol.

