Two male subjects with classical Fabry disease will be dosed in Cohort 1. Following the SMC recommendation to dose escalate to Cohort 2, which is subdivided into Cohort 2a (subjects who are antibody-positive to α -Gal A) and Cohort 2b (subjects who are antibody-negative to α -Gal A), 2 male subjects with classical Fabry disease will be dosed and safety data from these 2 subjects will be reviewed by the SMC. After SMC review, up to an additional 8 (4 subjects in Cohort 2a and 4 subjects in Cohort 2b) subjects may be recruited into Cohort 2 and if dose escalation is recommended, recruitment of subjects into Cohort 3 may commence. Dosing may continue in Cohort 2 until all 10 subjects have been dosed, unless it is concluded during the SMC review that it is more appropriate to dose in Cohort 3 rather than continuing dosing at the Cohort 2 dose level. Dosing in Cohort 3 and the remainder of Cohort 2 can be concurrent.

Following the SMC recommendation to dose escalate to Cohort 3, which is subdivided into Cohort 3a (subjects who are antibody-positive to α -Gal A) and Cohort 3b (subjects who are antibody-negative to α -Gal A), 2 male subjects with classical Fabry disease will be dosed and safety data from these 2 subjects will be reviewed by the SMC. After SMC review, up to an additional 8 (4 subjects in Cohort 3a and 4 subjects in Cohort 3b) subjects may be recruited into Cohort 3 and if dose escalation is recommended, recruitment of subjects into Cohort 4 may commence. Dosing may continue in Cohort 3 until all 10 subjects have been dosed, unless it is

concluded during the SMC review that it is more appropriate to dose in Cohort 4 rather than continuing dosing at the Cohort 3 dose level. Dosing in Cohort 4 and the remainder of Cohort 3 can be concurrent.

Following the SMC recommendation to dose escalate to Cohort 4, which is subdivided into Cohort 4a (subjects who are antibody-positive to α -Gal A) and Cohort 4b (subjects who are antibody-negative to α -Gal A), 2 male subjects with classical Fabry disease will be dosed and safety data from these 2 subjects will be reviewed by the SMC. After SMC review, up to an additional 8 subjects may be recruited into Cohort 4. Dosing may continue in Cohort 4 until all 10 subjects have been dosed, unless it is concluded during the SMC review that it is more appropriate to select a dose for dose expansion. Dosing in dose expansion and the remainder of Cohorts 3 and/or 4 can be concurrent.

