The dose considered to be tolerable and safe will be utilized in the dose expansion cohorts. After dose escalation has been completed, dose expansion will commence where up to 6 subjects will be enrolled into each of the dose expansion cohorts, which include patients with classical Fabry disease who are antibody-positive to α -Gal A, patients with classical Fabry disease who are antibody-negative to α -Gal A, female patients (female cohort) and patients who meet criteria for the renal (renal cohort) and cardiac (cardiac cohort) inclusion and exclusion criteria. The dose for the expansion cohorts may be reassessed if there are emerging safety considerations.

Anti α -Gal A Ab positive cohort: Up to 6 male subjects with classical Fabry disease who are antibody-positive to α -Gal A will be enrolled.

Anti α -Gal A Ab negative cohort: Up to 6 male subjects with classical Fabry disease who are antibody-negative to α -Gal A will be enrolled.

Female cohort: Up to 6 female subjects with classical Fabry disease will be enrolled.

Renal cohort: Up to 6 male or female subjects with symptomatic Fabry disease with a linear negative eGFR slope (estimated from at least 3 historical serum creatinine values [within 18 months, including the value obtained during screening visit]) of ≥ 2 mL/min/1.73 m²/year will be enrolled.

Cardiac cohort: Up to 6 male or female subjects with symptomatic Fabry disease with cardiac involvement, defined as either left ventricular hypertrophy (LVH) in 2D echocardiography or CMR (end diastolic septum and posterior wall thickness ≥ 12 mm) with no other explanation for LVH OR cardiac changes indicative of disease progression such as decreased global longitudinal strain on 2D strain echocardiography or low native T1 mapping on CMR will be enrolled. Subjects who have had a cardiovascular event in the 6-month period before screening may be excluded at the discretion of the Investigator.

[figure not shown]

Figure 2: Schema of Study Enrollment: Dose Escalation and Expansion

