 - ii) only male subjects with classical Fabry disease will be recruited during dose escalation and, to ensure that any residual enzyme level does not interfere with the measurement of enzyme levels produced by the cDNA transgene, either ERT-naïve subjects or subjects on a stable dose and regimen (defined as not having missed more than 3 doses of ERT during the 6 months prior to consent) or ERT-pseudo-naïve subjects who have previously been on ERT but have not received ERT treatment during the 6 months prior to baseline, will be allowed in the study
- c) ability to detect any safety signal

This sample size of 2 subjects per cohort will provide a 28% chance of observing at least one AE for events with a $\geq 15\%$ incidence. In addition, for an expanded cohort of 6 subjects (2 + 4), the sample size of 6 subjects will provide a 62% chance of observing at least 1 AE for events with a $\geq 15\%$ incidence.

Safety and tolerability of ST-920 infusion in each cohort will be assessed by incidence of TEAEs and serious AEs (SAEs). Other safety assessments will include monitoring liver tests for any AAV-associated elevation of liver enzymes, clinical laboratory tests (chemistry, hematology, urinalysis), vital signs, AAV clearance from tissues including plasma, urine, saliva, stool and semen (if applicable). Safety data from 24 subjects treated in the Sponsor's studies with AAV2/6 have, to date, not identified any dose limiting safety concerns with treatment of subjects at the starting dose proposed in this study. Therefore, 2 subjects per dose during the escalation is believed appropriate to limit the number of subjects who may be exposed to a suboptimal dose, and to maximize treatment of subjects at the dose that will optimize the benefit risk assessment. This is particularly pertinent, considering that it is very unlikely that a subject could be retreated with this technology should they not experience efficacy at the dose tested.

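### The up-to-48 sample size in Section 11.1 carries a breakdown that sums to 66, while the cohort maxima in Section 3.1 sum to 62

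*Combined protocol and SAP*

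**What the plan says.** Section 11.1 gives the total and itemises it in one sentence. It begins "This study will enroll up to 48 subjects (2 subjects in each of Cohorts 1, 2, 3, and 4 with potential enrollment", continues "of 4 additional subjects in Cohorts 1, 2a, 2b, 3a, 3b, 4a, and 4b, plus up to 6 subjects" and ends with the five expansion cohorts: the two defined by anti-α-Gal A antibody status, then the "female, renal, and cardiac cohorts". The same section says that the number has no statistical basis.

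Section 3.1 gives the same ceiling ("Up to 48 subjects who are ≥ 18 years of age and who satisfy all inclusion/exclusion criteria") but builds the cohorts differently. For the lowest dose, "Two male subjects with classical Fabry disease will be dosed in Cohort 1", and no additional places are named. For the next level, "Dosing may continue in Cohort 2 until all 10 subjects have been dosed"; Cohorts 3 and 4 have parallel sentences with the same limit of ten, each made of two subjects and then up to eight more. For expansion, "up to 6 subjects will be enrolled into each of the dose expansion cohorts", and five such cohorts are listed. The synopsis repeats the 48 and the cohort sizes of 3.1.

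Section 3.1 also gives two detection probabilities for an adverse event with an incidence of at least 15%: 28% with two subjects, and "for an expanded cohort of 6 subjects (2 + 4), the sample size of 6 subjects will provide a 62% chance".

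**The concern.** A parenthesis placed directly after a total is read as the parts of that total. Here the parts exceed it, and Section 3.1 gives a third number. A site, an ethics committee or the safety monitoring committee cannot tell from the text how many subjects each cohort may hold, or whether a third subject in Cohort 1 would be within the protocol.

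Cohort size matters because treatment-emergent adverse events are summarised overall and by dose and cohort (Section 11.2.2), and the secondary endpoints by dose and cohort (Section 11.2.3). The number in each cohort sets what each of those tables can show. Since 11.1 disclaims a statistical basis, the two detection probabilities in 3.1 are the only quantitative support for cohort size, so they should refer to cohorts that the design contains.

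**Working it through.** **Inputs.** From 11.1: two subjects in each of four cohorts; four more in each of seven cohorts or subcohorts (1, 2a, 2b, 3a, 3b, 4a, 4b); six in each of five expansion cohorts. From 3.1: Cohort 1 of two; Cohorts 2, 3 and 4 of up to ten each; five expansion cohorts of up to six. Both sections state up to 48.

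**Total from 11.1.** 4 × 2 + 7 × 4 + 5 × 6 = 8 + 28 + 30 = 66, which is 18 over 48.

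**Total from 3.1.** 2 + 10 + 10 + 10 + 5 × 6 = 62, which is 14 over 48.

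**Difference between the sections.** 66 − 62 = 4. These are the four additional Cohort 1 subjects that 11.1 allows and 3.1 does not mention. Without them, 11.1 also gives 62.

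**Simple variants that might recover 48.**
- Cohort 4 not opened: 66 − 10 = 56 (11.1) or 62 − 10 = 52 (3.1).
- Only two subjects in each escalation cohort, with full expansion: 8 + 30 = 38.

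None of these gives 48.

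**What the cap would imply.**
- Escalation filled as 3.1 allows: 2 + 30 = 32, leaving 48 − 32 = 16 places for 30 expansion slots, or 16 / 5 = 3.2 per cohort.
- Expansion filled first: 48 − 30 = 18 places for escalation, against the 32 that 3.1 permits.

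**Detection probabilities.** The chance of seeing at least one event of incidence 15% in n subjects is 1 − 0.85^n.
- n = 2: 1 − 0.85² = 27.75%. The plan says 28%, reproduced.
- n = 6: 1 − 0.85⁶ = 62.3%. The plan says 62%, reproduced.
- n = 10: 1 − 0.85¹⁰ = 80.3%. The plan gives no figure for this size, although it is the maximum for Cohorts 2, 3 and 4 in 3.1.

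Both stated percentages are therefore correct for the sizes they name. The mismatch is in the label. No escalation cohort in 3.1 is built as 2 + 4. Cohort 1 as described in 11.1 is, and the expansion cohorts have six subjects but are not 2 + 4.

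**The case against.** The strongest reply is that 48 is a ceiling throughout. The parts are conditional too: additional enrolment is only potential, and cohort sizes are maxima. The safety monitoring committee may move on before a cohort is full and may recommend changes to cohort enrolment. Table 1 also lets Cohort 3 receive the top dose in the range, so Cohort 4 might not be needed. A cap below the sum of optional maxima is ordinary in an escalation study. This stands, and it explains how 48 could be intended. It does not reconcile 11.1 with 3.1 on Cohort 1, and it does not make the parenthesis in 11.1 a correct description of 48. It supplies a mechanism but no numbers. One limit applies: the enrolment schema (Figure 2) is not visible in the text reviewed and the committee's charter is not supplied, so the missing allocation can be asserted only for the text available.

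A reader might also infer more than the documents support:
- **That 62% is wrong.** It is right for six subjects and fits the size of every expansion cohort. The omitted figure for ten is more favourable.
- **That 48 and the 2 + 4 label are left over from a smaller design.** Three cohorts of six plus 30 does give 48, but no such design appears in the documents.
- **That the renal and cardiac objectives rest on cohorts that may be squeezed.** Cardiac MRI is done in all subjects (Section 6.4.3), and eGFR is scheduled without cohort restriction (Appendix 1). No order of filling is stated among the expansion cohorts, and expansion may run alongside Cohorts 3 and 4.
- **That detection in expansion must fall.** With three subjects it would be 1 − 0.85³ = 39%, but that needs Cohorts 2, 3 and 4 all full. In that same case, if the expansion dose were that of one full escalation cohort, 10 + 16 = 26 subjects would share it, giving 1 − 0.85²⁶ = 98.5% at that dose.
- **That two subjects per dose is concealed as weak.** Section 3.1 discloses the 28% and gives other reasons for the choice.

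**Conclusion.** The inconsistency is real. The breakdown in 11.1 exceeds the stated 48 by 18, the maxima in 3.1 exceed it by 14, and the two sections differ by the four Cohort 1 places. These results need only addition of the plan's own numbers. The 16 places left for 30 expansion slots is a worst case, which assumes Cohort 1 at two and Cohorts 2, 3 and 4 all filled to ten under a binding cap of 48. The detection figures are arithmetically sound, and only the 2 + 4 label fails to describe Cohorts 2 to 4.

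The consequence is limited. All summaries are descriptive and the sample size has no power basis, so no test, error rate or estimate is affected. This is a consistency correction that should be made, not a defect that undermines the study.

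**What to change.** In Sections 3.1 and 11.1 and the synopsis:
1. Decide the maximum for Cohort 1 and state it identically in each place.
2. Rewrite the breakdown in 11.1 to match the cohort sizes in 3.1.
3. State the resulting sum of maxima: 62 if Cohort 1 stays at two, 66 if it may reach six.
4. If 48 is intended, say that it is an overall cap below that sum, and how places are divided between escalation and expansion.
5. Relabel the detection probabilities at 15% incidence by actual cohort size: 28% for two, 62% for six, 80% for ten. Drop the 2 + 4 label unless Cohort 1 is confirmed at that size.

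The cost is protocol wording. No extra subjects are needed and no analysis changes.

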11.2 Statistical Analyses

The primary objective of this study is to evaluate the safety and tolerability of ST-920. All statistical summaries will be descriptive in nature. All subjects who receive any portion of the ST-920 infusion will be included in the analyses. All analyses, summaries, and listing will be generated using SAS version 9.4 or later. Further analysis details will be provided in the statistical analysis plan (SAP).

11.2.1 Analysis of the Conduct of the Study

Enrollment, major protocol violations, and discontinuations from the study will be summarized by dose and cohort. The number of subjects who were enrolled, dosed, discontinued, and completed the study will be summarized.

Demographic and baseline characteristics will be summarized overall and by dose and cohort.

11.2.2 Primary Safety Analyses

The primary objective of this study is to evaluate the safety and tolerability of ST-920. Safety assessments will be performed on all subjects. All reported AEs will be coded to a standard set of terms using the Medical Dictionary for Regulatory Activities (MedDRA).

The incidence of TEAEs will be evaluated to address the primary endpoint of this study. A TEAE is any AE with an onset from administration of the study treatment through the last study visit, whether or not it is considered causally related to the study treatment. TEAEs will be

summarized overall and by dose and cohort. For each subject, the maximum reported severity of each AE will be used in the summaries by severity grade. In addition, summaries of all SAEs and AEs related to study treatment will be provided.

Additional safety evaluations will include:

- Routine hematology, chemistry, and liver tests, vital signs, ECG and ECHO
- Serial AFP testing and MRI of liver (or equivalent imaging modality) to monitor for liver mass.

For other safety evaluations, data will be summarized for each time point. Change from baseline values may be calculated for continuous parameters and summarized by time point. Shift-tables may also be constructed for selected parameters.

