A four-week staggering interval between dose cohorts will allow for appropriate time to collect safety data for the first two subjects in each cohort for the Safety Monitoring Committee to review and make recommendations to the Sponsor as to whether to dose-escalate, dose-de-escalate or add a cohort.

The duration of study participation will be up to 84 weeks for each subject divided into up to 8 weeks for screening, up to 24 weeks for baseline, and 52 weeks follow-up after dosing. Accrual is planned for 48 months.

The proposed evaluation period in this study is 52 weeks after ST-920 administration. This one-year safety evaluation of the study includes physical evaluation, ECG, ECHO, and hearing test, in addition to other routine clinical tests and biochemical safety evaluation (for further details, refer to [Section 6](#) and [Appendix 1](#)). The 52-week period will monitor for long-term expression and sustainability of the enzymatic activity produced by the cDNA, and may also give some preliminary information on Fabry-relevant parameters, such as renal function, cardiac function. In addition, at the end of the study period of 52 weeks, subjects will be encouraged to participate in an additional separate long-term follow-up study (of 4 years) for a total of at least 5 years from infusion for long term safety and durability of response monitoring.

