3.3 Baseline Period

Baseline assessments and procedures outlined in the Schedule of Events ([Appendix 1](#)) will be performed within 12 weeks prior to ST-920 infusion. The duration may be extended to 24 weeks for subjects whose visits are impacted by delays due to COVID-19. In subjects receiving ERT, assessments including α -Gal A levels, and Gb3 and lyso-Gb3 and immunogenicity samples will be taken at ERT trough levels, defined as 14 days (± 1 day) after the previous ERT administration. Two samples will be taken at baseline on 2 different days in the morning. For subjects not on ERT, two samples will be taken at baseline on 2 occasions with at least 14 days (± 1 day) between the 2 occasions. Documentation of dosing should be recorded in the electronic case report form (eCRF) and administration of all ERT should be obtained and recorded in the ERT Administration Log.

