9 SAFETY MONITORING AND ADVERSE EVENTS

9.1 Definitions

9.1.1 Adverse Event

An AE is any untoward medical occurrence in a patient or a clinical trial subject administered a medicinal product. An AE does not necessarily have a causal relationship with the administered treatment. The term can include any of the following events that develop or increase in severity during the course of the study:

- Any sign, symptom, or physical examination finding that worsens in nature, severity, or frequency compared to baseline, whether thought to be related or unrelated to the condition under study.
- Any laboratory abnormality that is clinically significant or that requires medication or hospitalization.
- All reactions associated with the use of the study treatment, including those occurring as a result of an overdose, abuse, withdrawal phenomena, sensitivity, or toxicity to the study treatment.
- Concurrent illness.
- Injury or accident.

A pre-existing condition is one that is present prior to or at the start of the study, and is to be reported as part of the subject's medical history. It should be reported as an AE only if the frequency, intensity, or the character of the condition worsens during study participation.

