9.2 Adverse Event Reporting Period

AEs will be monitored continuously during the study and reported from the time that the subject has provided written informed consent through the subject's last day of study participation. Subjects will be queried and events will be assessed at each clinic visit. Further assessments may be done if indicated for evaluating and monitoring the AE(s).

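### The TEAE definition has no worsening clause, so whether an AE that starts between consent and infusion and worsens after ST-920 counts toward the primary endpoint is left to site recording practice

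*Combined protocol and SAP*

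**What the plan says.** Section 11.2.2 sets the primary analysis: "The incidence of TEAEs will be evaluated to address the primary endpoint of this study". It then defines the event: "A TEAE is any AE with an onset from administration of the study treatment through the last study visit". The synopsis and the objectives table in Section 2.1 add nothing about worsening. Section 11.2 defers further detail to the SAP, and no SAP wording in the supplied text changes the definition.

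Three other places bear on the point.

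- **Collection period (Section 9.2).** AEs are "reported from the time that the subject has provided written informed consent", so recording starts well before dosing.
- **AE definition (Section 9.1.1).** It includes "events that develop or increase in severity during the course of the study". A separate sentence has worsening of a pre-existing condition reported as an AE, but limits pre-existing conditions to those present at or before the start of the study.
- **Severity tables (Section 11.2.2).** For each subject, "the maximum reported severity of each AE will be used in the summaries by severity grade".

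**The concern.** The AE definition recognises worsening, but the endpoint definition does not carry it over. Consider an event that begins after consent, is still present at infusion, and moves from Grade 1 to Grade 3 afterwards. It is already on the CRF with a pre-dose onset date. If the site updates that entry, the event fails the onset test and appears neither in TEAE incidence nor in the TEAE severity table. If the site opens a new entry dated at the worsening, the same clinical course is a TEAE.

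Such events are plausible. The pre-dose window contains baseline skin biopsies and, for some subjects, kidney biopsies (Appendix 1), withdrawal of migalastat where applicable (Section 4.1, criterion 6), and continued ERT. With about 20 to 30 sites, recording practice may differ between sites. Any resulting error runs one way: the primary safety result looks more favourable than it should.

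**Working it through.** **1. Length of the pre-dose window.** Section 3.1 divides participation into "up to 8 weeks for screening, up to 24 weeks for baseline, and 52 weeks follow-up after dosing". The plan's total reproduces: 8 + 24 + 52 = 84 weeks. Section 3.3 places baseline assessments "within 12 weeks prior to ST-920 infusion" and allows 24 weeks only for COVID-19 delays. The window from consent to infusion is therefore:

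- ordinary limit: 8 + 12 = 20 weeks
- with the COVID-19 extension: 8 + 24 = 32 weeks

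**2. Which clinical courses are affected.** This takes the start of the study to be consent, when AE reporting begins.

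| Course | Treatment under the text | TEAE? |
|---|---|---|
| Starts after infusion | AE with post-dose onset | Yes |
| Present at study start, worsens after infusion | Section 9.1.1 has the worsening reported as an AE | Yes, if dated at the worsening |
| Starts after consent, resolves before infusion | AE with pre-dose onset | No, rightly |
| Starts after consent, ongoing at infusion, worsens afterwards | No rule on a new entry or a new onset date | Depends on the site |

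Only the last row is the gap. For laboratory results, Section 9.3 has a Grade 3 or 4 increase from baseline reported as an AE, except when it belongs to a diagnosis already on the CRF. That covers many laboratory shifts, but the exception leaves out those tied to an earlier diagnosis.

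**3. The plan's own detection figures.** Section 3.1 gives a 28% and a 62% chance of seeing at least one AE of 15% incidence with 2 and 6 subjects. With 1 − (1 − 0.15)^n:

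- n = 2: 1 − 0.85² = 27.75%
- n = 6: 1 − 0.85⁶ = 62.29%

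Both reproduce. Now assume that a share f of such events are post-dose worsenings of AEs that began before dosing, and that none is re-entered. The chance of seeing at least one *counted* event is 1 − [1 − 0.15(1 − f)]^n:

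| f (assumed) | n = 2 | n = 6 |
|---|---|---|
| 0 | 27.8% | 62.3% |
| 5% | 26.5% | 60.2% |
| 10% | 25.2% | 58.1% |
| 20% | 22.6% | 53.6% |
| 30% | 19.9% | 48.6% |

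**4. Chance that at least one subject is affected.** Assume that a proportion p of subjects have such an event and that no site re-enters it. With 1 − (1 − p)^n:

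| p (assumed) | n = 2 | n = 6 | n = 48 | Expected subjects of 48 |
|---|---|---|---|---|
| 5% | 10% | 26% | 91% | 2.4 |
| 10% | 19% | 47% | 99% | 4.8 |
| 20% | 36% | 74% | over 99% | 9.6 |

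One subject is 1/6 = 17 percentage points of a 6-subject cohort and 1/2 = 50 points of a 2-subject group. Those shifts apply to the row for one event term or grade. The documents supply neither f nor p, and both tables are upper ends because they assume that no worsening is re-entered.

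**The case against.** The strongest reply is that Section 9.1.1 makes worsening compared with baseline an AE in its own right. Its natural onset is then the date of worsening, and a post-infusion worsening already meets the definition. This stands as a permitted reading: a site may record it so. It does not close the gap, because no section requires a new entry, and the explicit instruction on worsening concerns conditions present at study start. CRF completion instructions might settle the matter, but they are not among the documents.

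A reader might infer three stronger things that the documents do not support.

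- *These events are certainly lost.* The sentence on maximum severity might seem to imply one record per event. It is an ordinary tabulation rule, equally needed when a subject has several records of one term, and shows nothing about how records are opened.
- *The safety committee would be misled.* The stopping rules in Sections 3.5 and 10.3 depend on related Grade 3 or higher AEs, related SAEs, deaths and malignancies, not on the TEAE definition. The SAE and related-AE summaries in Section 11.2.2 are not worded as limited to TEAEs either.
- *Overall incidence moves by 17 or 50 points.* That needs a subject with no other TEAE in 52 weeks, after an infusion that Section 7.1.2 says may cause fever, chills or nausea.

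**Conclusion.** The point holds as a gap in the definition, not as a demonstrated loss of events. Read literally, the TEAE rule can omit an AE that starts between consent and infusion and worsens after ST-920, and whether it does depends on a recording choice that the protocol leaves open. Any error can only lower the reported TEAE incidence and severity. It bears mainly on term-level and grade-level counts of worsening that is neither serious nor judged related. Its size cannot be derived from the documents, and the figures above rest on assumed rates and on no re-entry. The study is descriptive, so no power or error-rate calculation is affected. The change should be made because this is the primary endpoint, cohorts are small and the remedy is cheap.

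**What to change.** Replace the definition in Section 11.2.2 with: *A TEAE is any AE with onset on or after the start of the ST-920 infusion, or any AE present before the infusion that worsens in severity (CTCAE grade) or becomes serious on or after it.* Carry the same wording into the SAP. Add a CRF completion instruction that such a worsening is recorded with its own start date and grade, so that the programmed rule does not depend on site habit.

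The cost is one sentence and one CRF instruction. The reported incidence may be slightly less favourable.
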